AE	Adverse Event/Adverse Experience
AEFI	Adverse Event Following Immunization
Anti-NP	Anti- nucleocapsid Protein
CC	Coordinating Centre
CIOMS	Council for international Organizations of Medical Sciences
CRF	Case Report Form
CTCAE	Common Terminology Criteria for Adverse Events
CTO	Clinical Trial Ontario
CCTS	Centre for Clinical Trial Support
CKD	Chronic Kidney Disease
COVID-19	Coronavirus 19
EC	Ethics Committee
ELISA	Enzyme Linked Immunosorbent Assay
HD	Hemodialysis
IB	Investigator's Brochure
ICH	International Council for Harmonisation of Technical Requirements for Pharmaceuticals for Human Use
IP	Investigational Product
DSMB	Data Safety Monitoring Committee
DSPC	1,2-distearoyl-sn-glycero-3-phosphocholine
eCRF	Electronic Case Report Form
pCRF	Paper Case Report Form
EDC	Electronic Data Capture

GCP	Good Clinical Practice
ICF	Informed Consent Form
MedDRA	Medical Dictionary for Regulatory Authorities
ORN	Ontario Renal Network
PD	Peritoneal Dialysis
PHI	Personal Health Information
PHIPA	Personal Health Information Protection Act
PI	Principal Investigator
PM	Product Monograph
QI	Qualified Investigator
RBD	Receptor-Binding Domain
REB	Research Ethics Board
RCT	Randomized Controlled Trial
SAE	Serious Adverse Event/Serious Adverse Experience
SC	Steering Committee
snELISA	Surrogate neutralization ELISA
SOP	Standard Operating Procedure
SRI	Sunnybrook Research Institute
SUADR	Serious and Unexpected Adverse Drug Reaction
TMF	Trial Master File
TDL	Task Delegation Log
USP	United States Pharmacopeia

Protocol Summary

Full Title	BOOST KIDNEY: A Multi-Centre 12 Month Parallel-Group Randomized Control Trial of BNT162b2 versus mRNA-1273 COVID-19 Vaccine Boosters in Chronic Kidney Disease and Dialysis Patients with Poor Humoral Response following COVID-19 Vaccination
Short Title	BOOST KIDNEY
Phase	II/III
Protocol Number	3750
Version Date	Version 5.0, Nov 5, 2021
Study Duration	1 year
Principal Investigator	[name]
Setting	Multicenter, 5 Dialysis Centres in Ontario and British Columbia, Canada
Number of Participants	300 participants
Study Design	Four arm parallel randomized controlled trial of BNT162b2 versus mRNA-1273, third dose of the COVID-19 vaccine stratified by initial two dose vaccine type
Main Inclusion Criteria	Dialysis and non-dialysis chronic kidney disease (Stage 3b-5)
Primary Outcome(s)	Evaluate effect of third dose COVID-19 vaccine booster (BNT162b2 versus mRNA-1273) on serologic SARS-CoV-2 response (Anti-RBD) at 1 month following booster dose.

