BTN162b2 at a two sided alpha of 0.05 assuming 25% response in the *BNT162b2* group based on the limited studies to date, we would require 58 participants in each study group. The 25% difference was determined by consensus by the Principal Investigators to represent a clinically important difference. Given the stratification by baseline vaccination received, there will be four study groups, requiring a sample size of 232 participants as shown in Table 2. A Bonferroni adjustment for the alpha will not be used. A similar sample size calculation is obtained if the nested (two) chi-squared tests for the primary outcome of this study are considered the equivalent of a logistic regression equation with the baseline initial vaccine received as the two covariates. Assuming approximately 25% response to a booster dose, and the general rule that 10 outcome events are required per covariate, and 10% drop out during the one month period of the primary outcome, a total sample size of 89 would be required. Capacity to enroll is higher, therefore the target sample size will be 300 participants to avoid under-powering the study, and will account for up to 10% participant loss to follow-up due to death or new COVID-19 infection during the 1 month follow-up period for the primary outcome.

Table 2: Potential sample size calculations based upon differences in Anti-RBD response observed between BNT162b2 and mRNA-1273 vaccines at a Power (1- β) of 80% and α 0.05

Clinically Significant Difference	BNT162b2 Response ^a	mRNA-1273 Response ^a	Power (1- β)	Alpha (α)	Required Sample Size	Required Total Sample Size (4 Groups)
30%	25%	55%	80%	0.05	41	164
30%	50%	80%	80%	0.05	39	156
30%	65%	95%	80%	0.05	27	108
25%	25%	50%	80%	0.05	58	232
25%	50%	75%	80%	0.05	58	232
25%	65%	90%	80%	0.05	43	172
20%	25%	45%	80%	0.05	82	328
20%	50%	70%	80%	0.05	93	372
20%	65%	85%	80%	0.05	73	292
15%	25%	40%	80%	0.05	152	608
15%	50%	65%	80%	0.05	170	680
15%	65%	80%	80%	0.05	138	552

^aDefined as reaching median convalescent serum levels of anti-RBD.

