10.3 Planned Analyses

The primary outcome will be evaluated at 30 days (1 month) following the study intervention.

Subsequent analyzes will be planned at other time points in the study (3 months, 6 months, and 12 months) following study intervention.

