10.5.1 Statistical Analysis of the Primary Outcome

An intention-to-treat analysis will be followed for the primary outcome. The primary outcome will be the proportion of patients who attain convalescent serum levels of Anti-RBD at 1 month (30 days) following third dose of vaccine. Two Chi-Squared test or Fisher's exact test will be used, one for those who received first two doses of *BNT162b2* and the second for those who received *mRNA-1273* for the first two doses. This study is powered to determine differences between the use of *mRNA-1273* vaccine and *BNT162b2* vaccine as the booster dose on the primary outcome based on a clinically significant difference of 25% as described above in the sample size considerations. An adjusted analysis with logistic regression modelling will be performed if imbalance in baseline characteristics is found to between study groups following stratified randomization. Individuals who develop new COVID-19 infection as determined by a positive Anti-NP serologic test or positive SARS-CoV-2 RT-PCR nasopharyngeal swab during the study will be excluded from analysis of the primary outcome.

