10.5.2 Statistical Analysis of Secondary Outcomes

Secondary outcomes will include the proportion of patients who attain Anti-Spike median convalescent serum at 1 month (30 days) following third dose of vaccine. Differences in relative antibody levels (Anti-Spike and Anti-RBD) and neutralizing antibodies between study groups will be assessed through the Mann-Whitney test. The relative levels of antibodies will be tracked

longitudinally for each patient permitting analysis of SARS-CoV-2 antibody kinetics following vaccination and will be assessed through a mixed-effects repeated measures model with random intercepts and fixed covariates following log transformation of relative ratios, which will be exploratory. Differences in serial levels in relative antibody levels will be compared through a mixed effects model as above. Similar to the primary outcome, those with a new positive Anti-NP serologic test or COVID-19 nasopharyngeal swab during the study will be excluded from analysis. An intention to treat analysis will be followed, although an exploratory per protocol analysis may also be reported.

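### The infection exclusion for the 1-month primary outcome has no cut-off at the 1-month sample, and the reduced set is still labelled intention-to-treat

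*Combined protocol and SAP*

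**What the plan says.** The title describes "A Multi-Centre 12 Month Parallel-Group Randomized Control Trial of BNT162b2 versus mRNA-1273 COVID-19 Vaccine Boosters". Section 10.3 fixes the primary time point: "The primary outcome will be evaluated at 30 days (1 month) following the study intervention". It then adds: "Subsequent analyzes will be planned at other time points in the study (3 months, 6 months, and 12 months) following study intervention".

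Section 10.5.1 opens with "An intention-to-treat analysis will be followed for the primary outcome". It closes by removing participants whose new infection is shown by a "positive Anti-NP serologic test or positive SARS-CoV-2 RT-PCR nasopharyngeal swab during the study will be excluded from analysis of the primary outcome". Section 7.2.3 states the same exclusion, also without a time limit, and gives its purpose: to keep natural infection from contaminating the results.

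Section 10.2 is narrower. Its allowance of up to 10% covers loss due to "death or new COVID-19 infection during the 1 month follow-up period for the primary outcome".

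Section 10.5.2 repeats the rule for the secondary outcomes: "those with a new positive Anti-NP serologic test or COVID-19 nasopharyngeal swab during the study will be excluded from analysis". The next sentence reads: "An intention to treat analysis will be followed, although an exploratory per protocol analysis may also be reported". The statistical analysis row of the Protocol Summary also describes the primary analysis as intention-to-treat.

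Table 1 schedules Anti-NP at enrolment and at 1, 3, 6 and 12 months, so infections will go on being detected long after the primary sample.

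**The concern.** An infection acquired in month 5 cannot change an anti-RBD level measured in month 1, so the contamination rationale in 7.2.3 gives no reason to discard that result. Sections 10.5.1 and 7.2.3 nevertheless discard it. Three things follow.

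- **The primary set is not fixed.** One analyst working at month 1 and another at month 12 would follow the same text and get different denominators.
- **Membership depends on an event after the endpoint.** That event may relate to the booster response or to the arm. Section 3.2 lists between-group differences in infection as an outcome. Section 5.5.2 unblinds participants at 30 days, so later infections arise when they know which vaccine they received.
- **The label is wrong.** A set that drops randomized participants for a post-randomization event is not intention-to-treat, even if the drop stops at month 1. A report using the label would misdescribe its denominator.

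In 10.5.2 the rule removes the whole participant, so antibody samples drawn before the infection are lost too.

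**Working it through.** **Inputs from the documents.** 25% vs 50% response, two-sided alpha 0.05, 80% power, 58 per group and 232 in total, target 300, 10% loss in month 1 (all 10.2); 1:1 allocation within initial-vaccine stratum (4.1, Figure 2 caption); five antibody samples per participant (Table 1).

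**Assumed, because the documents do not say.** Equal strata (75 per group), the 10% allowance fully spent (300 × 0.9 = 270), and a share L of those 270 infected after the 1-month sample.

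**1. Reproduce the plan's figure.** n = [1.960·√(2·0.375·0.625) + 0.842·√(0.25·0.75 + 0.50·0.50)]² / 0.25² = (1.342 + 0.557)² / 0.0625 ≈ 57.7, rounded up to 58; 4 × 58 = 232. The stated figure is confirmed.

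**2. Loss of 1-month results.** n per group = 270(1 − L)/4. Power = Φ{[0.25√n − 1.342]/0.661}. The last column is the exact power of the chi-squared test with n rounded down to a whole number.

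| L | results removed | n per group | power (normal) | power (exact) |
|---|---|---|---|---|
| 0% | 0 | 67.5 | 85.9% | 85.7% |
| 5% | 14 | 64.1 | 84.1% | 84.9% |
| 10% | 27 | 60.8 | 82.0% | 81.8% |
| 14.1% | 38 | 58.0 | 80.2% | 79.9% |
| 20% | 54 | 54.0 | 77.3% | 77.9% |
| 30% | 81 | 47.2 | 71.5% | 71.2% |

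The break-even is 1 − 232/270 = 14.1%. If none of the allowance is spent, L = 20% still leaves 300 × 0.8/4 = 60 per group, with power of about 82%.

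**3. Selection on response.** Let r1 and r0 be the later infection rates in responders and non-responders, the same in both arms (assumed). The analysed response is p(1 − r1)/[p(1 − r1) + (1 − p)(1 − r0)].

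- r1 = 10%, r0 = 20%: 25% vs 50% becomes 27.3% vs 52.9%, a difference of 25.7 points.
- r1 = 10%, r0 = 30%: it becomes 30.0% vs 56.25%, a difference of 26.3 points.

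**4. Secondary antibody samples.** An infection first detected at month 3, 6 or 12 discards 2, 3 or 4 samples drawn before the first evidence of it. Spread later infections evenly over months 1 to 12 (assumed), with weights 2/11, 3/11 and 6/11. The mean is (2·2 + 3·3 + 6·4)/11 = 3.36 per person. With L = 10%, 27 people lose 27 × 5 = 135 samples. About 91 of these (27 × 3.36) precede first evidence, so a sample-level rule would drop about 44.

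**5. Choice of primary set.** If a share m is infected in month 1 and all of them then count as responders (assumed), keeping them changes p to p + m(1 − p). With m = 2% the comparison is 26.5% vs 51.0% (24.5 points). With m = 5% it is 28.75% vs 52.5% (23.75 points).

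**The case against.** The best defence is that a 1-month window was meant. Section 10.2 budgets infection loss for that month only, and 10.3 reads the outcome at 30 days and treats the other visits as later analyses. Section 10.5 also leaves a final analysis plan to be developed, which could set a data cut. All of this is fair, so a reader should not infer that the sponsor has settled on a 12-month exclusion. It does not remove the problem: 10.5.1 and 7.2.3 are the operative rules, neither carries the limit, and they are not reconciled with 10.2.

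The longer window also buys something. A reader might infer that a result cannot be contaminated if infection was detected only after the sample. The documents do not support that. Section 7.2.3 puts Anti-NP sensitivity at about 79% and testing happens only at visits, so an infection that began before the 1-month sample may first show at month 3. The literal rule would catch some of these. For the same reason, not every sample counted in step 4 as preceding first evidence is clean.

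The likely size is small. Section 4.1 expects low incidence. Section 2.1 gives a cumulative 5.73% in Ontario dialysis patients, although its printed counts do not reproduce that percentage. Used purely as an assumed value of L, it removes 270 × 0.0573 ≈ 15 results and leaves about 63 per group, with power of about 84%.

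A spurious arm difference can be constructed. With 50% response in both arms, 10% of responders infected later, and 20% vs 40% of non-responders infected later, the analysed rates are 52.9% and 60.0%. Nothing in the documents supports infection rates that differ by arm in this way. The example shows what the rule permits, not what to expect.

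Finally, the label sits in the same paragraph as the exclusion, so nothing is hidden. That makes it a naming error, but one that would carry into the report.

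**Conclusion.** The point stands and should be fixed. As written, the primary exclusion has no end at the 1-month sample, conflicts with the 1-month allowance in 10.2, and leaves a set that is not intention-to-treat. The participant-level rule in 10.5.2 discards usable antibody samples. Confidence is high for the textual mismatch. The size of the harm is conditional and probably modest, because it rests on assumed later infection rates, equal strata and a fully spent allowance.

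Two stronger readings are not supported. A reader might infer that the trial is underpowered, but the sample size reproduces and the margin above 232 is used up only beyond about 14% later infection. A reader might also infer that infected participants are removed from the infection, hospitalization and death outcomes. The context points the other way: 7.2.3 gives a contamination rationale, the methods in 10.5.2 are all for antibodies, and 10.5 lists the clinical outcomes without an exclusion.

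**What to change.** 1. In 10.5.1 and 7.2.3, limit the primary exclusion to infections first detected up to and including the 1-month sample, consistent with 10.2.
2. In 10.5.2, drop only antibody samples drawn at or after the first evidence of infection (new Anti-NP positivity relative to enrolment, or positive RT-PCR) and keep earlier ones.
3. Call the infection-excluded set something other than intention-to-treat, for example modified intention-to-treat, here and in the Protocol Summary. Beside it, report the 1-month outcome in all randomized participants with a result, regardless of infection.

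The cost is a few sentences and one supporting table. Anti-NP is already scheduled at every visit needed, so no new samples are required. The downside is that a few infections that preceded the 1-month sample but were first detected later would stay in the primary set. A sensitivity analysis that also excludes participants first Anti-NP positive at month 3 would show whether this matters.

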10.5.2 Statistical Analysis of Secondary Outcomes

Secondary outcomes will include the proportion of patients who attain Anti-Spike median convalescent serum at 1 month (30 days) following third dose of vaccine. Differences in relative antibody levels (Anti-Spike and Anti-RBD) and neutralizing antibodies between study groups will be assessed through the Mann-Whitney test. The relative levels of antibodies will be tracked

longitudinally for each patient permitting analysis of SARS-CoV-2 antibody kinetics following vaccination and will be assessed through a mixed-effects repeated measures model with random intercepts and fixed covariates following log transformation of relative ratios, which will be exploratory. Differences in serial levels in relative antibody levels will be compared through a mixed effects model as above. Similar to the primary outcome, those with a new positive Anti-NP serologic test or COVID-19 nasopharyngeal swab during the study will be excluded from analysis. An intention to treat analysis will be followed, although an exploratory per protocol analysis may also be reported.

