4 STUDY DESIGN

4.1 General Design

The BOOST-KIDNEY study is a prospective, investigator and participant blinded randomized four parallel arm controlled study for CKD stage 3b-5 patients to evaluate the effect of a booster dose of vaccine on immunogenicity among those who did not respond defined as not reaching convalescent serum levels of Anti-RBD, or who exhibit declining antibody titers below the convalescent serum level of Anti-RBD. Enrolment will prioritize patients on dialysis but inclusion criteria will also include non-dialysis CKD stage 3b-5. Patients who are already participating in the study “Determining the Safety and Efficacy of COVID-19 Vaccination in the Chronic Kidney Disease Population” (CTO Protocol Number 3604) and have been found to have poor humoral response to COVID-19 vaccination will prioritize for recruitment. However, if a booster dose of COVID-19 vaccine is approved for the study population during the study period, patients will be eligible without serologic evaluation.

Patients will be randomized to mRNA-1273 SARS-CoV-2 Vaccine (*SPIKEVAX®/Moderna*), or BNT162b2 mRNA Covid-19 Vaccine (*COMIRNATY®/Pfizer-BioNTech*) administered by a trained vaccine administrator. Information on prior vaccines received will be recorded, and patients may have received either mRNA-1273 SARS-CoV-2 Vaccine (*SPIKEVAX®/Moderna*), or BNT162b2 mRNA Covid-19 Vaccine (*COMIRNATY®/Pfizer-BioNTech*) for their initial two doses of vaccine. Patients will be stratified by their initial vaccine type (BNT162b2 or mRNA-1273) prior to randomization, which will result in four study groups as shown in Figure 2.

A placebo arm is not included in this study as it was not felt to be ethically justified, but comparison will be made to participants not receiving a booster vaccine enrolled in CTO Protocol Number 3604 who choose not to participate. Similarly a primary outcome of COVID-19 infection

or hospitalizations was not chosen given the low incidence of COVID-19 infections in Canada due to high vaccination rates in the country.

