6.1.3.1 Identification of Individuals with Suboptimal Humoral Response

Patients enrolled in the pilot study “Determining the Safety and Efficacy of COVID-19 Vaccination in the Chronic Kidney Disease Population” (with Protocol CTO number 3604) or who are interested in the study who are found to have poor humoral response will be determined to be eligible for the trial by assessing their most recent antibody levels drawn at a minimum 1 month following their second dose of COVID-19 vaccine. Upon study enrolment SARS-CoV-2 antibodies against anti-Spike, anti-RBD, and anti-NP will be performed to exclude evidence of recent COVID-19 infection and confirm anti-RBD levels below convalescent serum levels.

Antibodies targeting the full-length spike protein (anti-spike) and its Receptor Binding Domain (anti-RBD) measured humoral response to SARS-CoV-2 vaccination and/or natural infection while antibodies to the nucleocapsid protein (anti-NP) detected natural SARS-CoV-2

infection, as this antigen is not targeted by the BNT162b2 vaccine. Antibody levels are reported as relative ratios to a synthetic standard included as a calibration curve on each assay plate.

Thresholds for positivity (seroconversion) were determined by aggregating data from negative controls and calculating the mean + 3 standard deviations. The median level of convalescent serum is determined by comparison to the median levels of convalescent serum taken 21-115 days post symptom onset in patients with COVID 19. The convalescent serum patients (n=211) were obtained from the Toronto Invasive Bacterial Diseases Network (REB studies #20-044 Unity Health, #02-0118-U/05-0016-C, Mount Sinai Hospital). had a median age of 59 years, 115/211 (55%) were male and included patients with mild (defined as not requiring hospitalization), moderate, and severe disease severity.

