Seroconversion thresholds represent a positive serology test and are 0.19, 0.186, and 0.396 for anti-spike, anti-RDB, anti-NP antibodies respectively at a dilution of 0.0625. The median level of antibody in convalescent serum taken 21-115 days post-symptom onset in those infected with COVID-19 is considered a robust antibody response and is 1.38, 1.25, and 1.13 for anti-spike, anti-RBD, and anti-NP antibodies, respectively. All patients with anti-RBD below the level of convalescent serum at last serologic sampling will be eligible for the study which will be confirmed by serology taken upon enrolment in the study or already available due to registration in “Determining the Safety and Efficacy of COVID-19 Vaccination in the Chronic Kidney Disease Population” (CTO Protocol No. 3604).

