7 STUDY SCHEDULE AND PROCEDURES

7.1 Study Procedure

Participants who meet study eligibility criteria and consent to participate will be enrolled in the study. At study enrolment baseline, serum will be collected for SARS-CoV-2 serology, neutralizing antibodies and in a subset determined by the Investigator, PBMC will be collected for assessment of cellular immunity at Sunnybrook Health Sciences Centre or University Health Network prior to receiving the booster dose. Patients who are already participating in the study “Determining the Safety and Efficacy of COVID-19 Vaccination in the Chronic Kidney Disease Population” (CTO Protocol Number 3604) and have been found to have poor humoral response to COVID-19 vaccination will be prioritized for recruitment. However, if a booster dose of COVID-19 vaccine is approved for subsets of the study population or the study population at large during the study period, patients remain eligible for randomization without serological confirmation of low antibody titres.

Vaccine will be administered by an individual trained in vaccine administration at the site.

Following vaccination, participants will be asked about adverse symptoms related to COVID-19 vaccination through a questionnaire at 48 hours -14 days either in person in the dialysis unit or by telephone and at 1 month post third dose.

Following the intervention with either third dose of booster vaccine, the participant will have blood collection for Anti-SARS-CoV-2 IgG antibodies targeting the full length spike protein, RBD, nucleocapsid protein at 1 month, 3 months, 6 months, and 12 months following receipt of the booster dose. For feasibility, neutralizing antibodies will only be performed at 1 month following third dose. Non-dialysis participants may have bloodwork testing as part of routine

clinical care at each time point to determine if the booster vaccine dose has impacted kidney function including a serum creatinine and a spot urine micro-albumin creatinine ratio.

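### The anti-Spike responder outcome has no baseline condition, so participants already at or above 1.38 at enrolment count as responders and dilute the booster comparison

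*Combined protocol and SAP*

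**What the plan says.** The outcome is set in section 10.5.2: "Secondary outcomes will include the proportion of patients who attain Anti-Spike median convalescent serum at 1 month (30 days) following third dose of vaccine". It carries no condition on the value before the booster, and the word for reaching the level is not defined. The section also says that intention to treat is followed.

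The cut-offs are in section 6.1.3.1: the convalescent median "is considered a robust antibody response and is 1.38, 1.25, and 1.13 for anti-spike, anti-RBD, and anti-NP antibodies, respectively". Anti-Spike (1.38) and anti-RBD (1.25) therefore have separate thresholds.

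Entry uses only one of them. Section 6.1.3.1 says: "All patients with anti-RBD below the level of convalescent serum at last serologic sampling will be eligible for the study". The enrolment sample is taken to look for recent infection and to "confirm anti-RBD levels below convalescent serum levels". Anti-Spike is measured in that sample ("Upon study enrolment SARS-CoV-2 antibodies against anti-Spike, anti-RBD, and anti-NP will be performed"), and Table 1 schedules it at enrolment, but no section makes it an eligibility condition.

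If a booster is approved for the study population, the screen falls away. Section 4.1 says that "patients will be eligible without serologic evaluation", and section 7.1 that "patients remain eligible for randomization without serological confirmation of low antibody titres". Section 5.5 is to the same effect.

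**The concern.** For the primary outcome, the normal entry rule does useful work: everyone starts below 1.25 on anti-RBD, so being at or above 1.25 one month later is a change of status. The anti-Spike outcome takes over the responder idea without that safeguard. A participant with anti-RBD below 1.25 and anti-Spike at or above 1.38 meets the rule, enters with the anti-Spike level already reached, and is counted as a responder unless the value falls.

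The design makes such participants plausible, because it deliberately includes people who once reached convalescent levels and have declined (sections 2.3 and 4.1). Some may have crossed one cut-off and not the other. If the approval clause is used, people who are above both cut-offs may enter too.

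Two things are at stake. The difference between boosters is pulled towards zero, and the reported proportion attaining convalescent anti-Spike includes people whose status the booster did not change.

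**Working it through.** **The plan's own figure first.** Section 10.2 gives 58 per group for 25% v 50%, two-sided alpha 0.05, 80% power (anti-RBD). The pooled-variance formula is

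n = [1.960 × √(2 p̄(1 − p̄)) + 0.842 × √(p₁(1 − p₁) + p₂(1 − p₂))]² / (p₂ − p₁)²

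With p₁ = 0.25, p₂ = 0.50 and p̄ = 0.375 it gives 57.7, rounded up to 58; 4 × 58 = 232. Both stated figures reproduce. The documents give no sample size or power for anti-Spike.

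**Inputs**
- Target 300, with up to 10% lost by 1 month (section 10.2): 300 × 0.90 = 270, and 270 / 4 = 67.5, taken as 67 per group. This assumes equal prior-vaccine strata.
- Response among those below 1.38 at enrolment: 25% v 50%. This is an assumption, borrowed from the anti-RBD planning rates.
- s, the share of each arm at or above 1.38 at enrolment: not in the documents, so a range is shown. Those participants are assumed still to be at or above 1.38 at 1 month.

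**Formulas**
- Observed rate as written: s + (1 − s)p.
- Observed difference as written: (1 − s)(p₂ − p₁).
- Restricted comparison: p₁ v p₂ with 67(1 − s) per group, rounded.

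Example, s = 20%: 0.20 + 0.80 × 0.25 = 40% and 0.20 + 0.80 × 0.50 = 60%. The difference is 20 points instead of 25. The restricted set has 67 × 0.80 = 53.6, so 54 per group.

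**Results**, by exact binomial enumeration of the uncorrected chi-squared test at two-sided 0.05, within one prior-vaccine stratum:

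| s | Rates as written | Difference (points) | Power as written, 67 per group | Restricted n per group | Power restricted |
|---|---|---|---|---|---|
| 0% | 25.0 v 50.0% | 25.0 | 86% | 67 | 86% |
| 5% | 28.75 v 52.5% | 23.75 | 80% | 64 | 85% |
| 10% | 32.5 v 55.0% | 22.5 | 74% | 60 | 82% |
| 20% | 40.0 v 60.0% | 20.0 | 63% | 54 | 78% |

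Across this range the restricted comparison has more power on fewer people, because those removed contribute the same expected result to both arms. The normal-approximation formula agrees closely: 81%, 75% and 64% as written against 84%, 82% and 77% restricted for s = 5%, 10% and 20%.

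**Other response rates.** The direction is the same from the other 25-point rows of Table 2. By the normal approximation at s = 20% and 67 per group, 50% v 75% gives 72% as written against 77% restricted, and 65% v 90% gives 86% against 88%. The loss is smaller when response is high.

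**The case against.** **The size is unknown.** This stands. Neither s nor an anti-Spike response rate is in the documents. Both cut-offs are medians from the same convalescent cohort and both antibodies are measured in the same samples, so people low on anti-RBD will tend to be low on anti-Spike. Under the normal screen s may be small, and at 5% the loss is about 5 points of power. A reader might push s to 40%, where the same calculation gives 43% as written, and conclude that the comparison is badly underpowered. Nothing in the documents supports a share of that size.

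**It is a different estimand, not a bias.** This also stands. The proportion at or above 1.38 among all randomised participants is a legitimate intention-to-treat quantity: how many are at a robust level after each booster. Its weakness is that it does not isolate the change that the booster made. A reader might infer a false-positive risk. There is none from this source, because randomisation balances s in expectation.

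**The wording may already exclude these people.** Attaining a level can be read as newly reaching it. The plan does not say so, and the two readings use different denominators, which is a reason to define the term.

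**Other analyses cover it.** Largely true. Section 10.5.2 also compares anti-Spike levels by the Mann-Whitney test and by a mixed model on log ratios, and neither uses 1.38. They do not replace a reported responder percentage.

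**The stakes are low.** Agreed. The outcome is secondary, section 10.2 powers only the anti-RBD comparison, and section 10.5 leaves the final analysis plan to be developed.

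**Conclusion.** The gap is real and minor. Eligibility places no limit on anti-Spike, and the responder outcome has no baseline condition, so participants at or above 1.38 at enrolment would count as having attained the level in either arm. The expected difference shrinks by (1 − s) and both reported rates rise. With s of 5% to 20%, the illustrative 25-point difference becomes 23.75 to 20 points, and power goes from 80% to 63% as written against 85% to 78% restricted. These figures rest on the borrowed 25% v 50% rates, equal strata, 67 evaluable per group, and participants above 1.38 staying there.

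A reader might infer that everyone enrolled under the normal rule is affected. Only discordant participants are: anti-RBD below 1.25 with anti-Spike at or above 1.38. The approval clause could raise their number, and it would open the primary anti-RBD outcome to the same dilution, but the documents do not say how many would enter that way. Nor do they support calling the all-randomised proportion invalid.

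**What to change.** In section 10.5.2:

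1. Define the anti-Spike responder comparison, within each prior-vaccine stratum, as anti-Spike at or above 1.38 at 1 month among participants whose enrolment anti-Spike was below 1.38.
2. Report by arm the number at or above 1.38 at enrolment, and show their 1-month results separately.
3. Keep the all-randomised proportion as a supporting intention-to-treat summary.
4. State that the enrolment sample in Table 1 is still drawn when the approval clause waives serologic screening, and how a missing enrolment value is handled.

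The cost is a few sentences. Anti-Spike is already scheduled at enrolment, so no new sample is needed. The restriction uses a value from before the booster, so the randomised comparison is preserved. The downside is a somewhat smaller denominator for this one secondary outcome: 64, 60 or 54 per group instead of 67 for s = 5%, 10% or 20%.
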